Those whom are ineligible in this study are: those that do not give consent and/or assent to participate; those that do not identify as tribal members of Mescalero Apache, Jemez Pueblo and Ramah Navajo or as the family member of someone that identifies as Mescalero Apache, Jemez Pueblo and Ramah Navajo; children and that are not in the targeted range of fourth grade. The inclusion for the comparison group follows the same criteria, in having a child from the fourth grade and being tribal members, but who decide not to participate in the FL/CP program and are willing to assent/consent to take the pre and post-tests.

6) Number of Subjects (Recruitment Target)

Target number of participants is 12 child participants and at least one parent/guardian in the family for a total of two members from one family, an expected 12 families annually for an overall total of 48 family participants over four years per community. Because of expected drop of 1-3 families (known attrition from our feasibility trials) by end of the twelfth session, we will initially recruit 13-14. Comparison participant numbers will be 12 children and 12 parent/or guardians.

The expected sample size for the families will total 576 participants from Fiscal Years 1, 2, 3, and 4 only (3 data collection waves total). Each wave per year will recruit 12 Program and 12 Comparison families. Based on our multiple pilots with each tribe, we have determined a Family will be represented by at least 1 parent with 1 child; thus our participant totals (program & comparison) are 24 youth and 24 parents per tribe per year (48 participants X 3 tribes X 4 years (data collection waves) = 576). Furthermore, based on previous pilots with each tribe it is anticipated the sample will enroll more females than males at an approximate ratio of 70:30 and the majority of participating parents to be female.

Table 2. Data Collection	FY01 (2014- 2015)		FY02 (2015-2016)		FY03 (2016-2017)		FY04 (2017-2018)		FY05 (2018-2019)	
	Sep 14'	Mar 15'	Sep 14'	Mar 15'	Sep 14'	Mar 15'	Sep 14'	Mar 15'	Sep 14'	Mar 15'
*Wave 1	Pre- Test	Post- Test		1-Yr Follow up						
*Wave2			Pre- Test	Post-Test		1-Yr Follow up				
*Wave3					Pre- Test	Post-Test		1-Yr Follow up		
*Wave4							Pre- Test	Post-Test		1-Yr Follow up

* Each data collection wave (4 Waves totaling 288 families) includes three data collection points (pre, post, and 1 Yr Follow Up) for intervention & comparison families.

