WAVE TOTAL = 12 Program Families (12 families X 3 tribes X 4 waves = 144 families (144 students + 144 parents = 288 participants)

= 12 Comparison Families (12 families X 3 tribes X 4 waves = 144 families (144 students + 144 parents = 288 participants)

7) Recruitment Methods

Members of the tribal research team will work with the schools from each community and will identify the potential participants from the fourth, grades of these schools. Letters will be sent home with the fourth grade children and TRT members; and by TRT members presenting to the children in their classrooms on the Family Listening Program and how interested students may participate in this research project. The attached recruitment letter will have minor changes by TRT members who will insert their contact information specific to each community. (see Attachment A). Should a child express an interest then the research team member will follow-up with the parents of the child and the components of the Family Listening/Circle Program will also be shared.

Based on previous pilots with all tribes, all youth participants will be between 9-10 years of age and be enrolled in 4th grade. Evidence of community support and the ability to recruit participants, implement measurement and protocols, and oversight exists through the previous feasibility trials and earlier grants and collaborative work. . At a minimum, Mescalero has 5 years, Ramah has 11 years and Jemez has 14 years of NIH research funded experience with the UNM Center for Participatory Research; which resulted with this multi-tribal application to test effectiveness. The current partnering opportunity stems largely from feasibility and development efforts, multiple pilot projects, presentations and publications. The Tribal Research Teams (TRTs) themselves, are also direct outcomes of previous Community-Based Participatory Research (CBPR) projects that have elevated Advisory Councils (typical of most CBPR projects) to more action-oriented shared leadership bodies that co-design, co-implement and co- translate findings while providing direct research oversight through tribally-driven research and approval processes, and a multi-tribal/academic partnership connected together by UNM-CPR.

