Leaders, managers, educators, and/or staff. For the third aim of the grant, in the first program year, the UNM and community TRTs will conduct a review of community organizations and prevention and youth programs in the community and at schools. From this review of programs, the pool of managers and educators will be identified.

Community/traditional leaders may not be affiliated with programs therefore we will rely on the community knowledge and connections of the Tribal Research team members to recruit these leaders. Starting in year 1 and continuing through year 5, TRT members will recruit those identified by phone or face-to-face communication. The consent process as detailed above will occur immediately prior to the individual interview. Potential participants will be contacted and interviews will be conducted during the fourth quarter of each program year. The described recruitment process is the preferred method by the respective TRTs because it ensures a) involvement with this study is entirely participatory and voluntary and b) an understanding of the research involved by potential participants is obtained and discussed to satisfaction of TRT members, with UNM research team members present and available as necessary.

8) Study Timelines

Attached updated study timeline (see Attachment B)

9) Study Endpoints

Our final endpoint will be the collection in year 5 of the one-year post-test of the final program implementation groups in year 4. A potential reason to terminate the study would be when there are no voluntary family participants.

10) Research Setting

Describe the sites or locations where your research team will conduct the research.

The Family Listening/ Circle Program will be conducted in three tribal communities in New Mexico. The program is a dinner program with four facilitators and 12 families (child/parent/invited elders) held in tribal facilities, such as a school, a library, an

(09.22.2014)

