- c) Tribal research team members, who are already trained, will administer pre/post and one-year post surveys with parent and child participants, and with comparison parents and children. UNM research team will provide support. We have chosen not to include elders in the quantitative instruments, as their primary (and sometimes only) language is the tribal language; elders do participate in mid-program and end of program discussions on program satisfaction and how program can continue to meet family needs. The post-tests include two open-ended “360” questions: asking parents how their child and family have changed, and asking children, how their parent and family have changed. For this RO1, we have adopted the use of laptops for data input, at the request of the IRB to provide greater guarantee of confidentiality for the children and parents.
- d) Tribal facilitators will administer the twelve two to 2 1/2 hour sessions of the prevention/intervention family program UNM research team will provide support. Each of the tribes has trained facilitators (who are teachers, educators, behavioral health counselors, and prevention and cultural/language staff), with four needed for each FL/CP program implementation, two working with the adults and two working with the children during their breakout groups, and working together when the families are sharing what they learned. Each year, at least two trained facilitators will participate (overseeing the facilitation) and the TRTs will recruit and train others in subsequent years to expand the pool of tribal members knowledgeable about the program overtime. During the previous pilot funding, the UNM team provided training and support during the sessions. In this RO1, the tribal facilitators are trained and will be leading the curriculum. UNM team members will join periodically to provide support and to observe. Two of the facilitators in each group have taken the CITI training because they are also involved in data collection. All have been trained in confidentiality issues, motivational interviewing, facilitation of groups, and know the behavioral back-up protocols to refer children or parents if needed. (DSMP attached).

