- e) The intervention curriculum follows the exact curriculum developed in the three tribal communities during the pilot funding. Based on the pilot experience, the curriculum has been formalized into a systematic common format, with twelve weekly sessions, held at dinnertime for 2 and 2 1/2 hours. The program is held in tribal facilities, such as a school, a library, an intergenerational center, and there is no other business taking place at that time. Occasionally a session is postponed to the next week due to tribal community events. The twelve session themes are:

Welcoming
Tribal History (Part I)
Tribal History (Part II)
My Family
Tribal Way of Life
Community Vision
Community Challenges
Communication, Help Seeking & Problem Solving
Recognizing Types Of Anger & Managing Anger
Being Different & Positive Relationships
Building Social Support
Making A Commitment & Community Project Presentations

Each session starts with a collective dinner with families eating together (as a prevention strategy in itself), they then practice their Indian and clan names. The sessions are led by facilitators in their own language or bilingually, as interactive activities. The facilitators then divide the families into children and adult groups into separate rooms to address the theme of the session (with two facilitators per each group), and they then return together at the end of the session to share their learnings. For example in the Visioning session, the adults create their pictorial visions using crayons and markers, the children create their visions, and then they get back together as a whole group of 12 families to share their visions from different generational perspectives. All the children are given a chance to share first, with some parents and elders sharing after. The sessions always end with the children and adults writing in their journals which are individual pages that they then put in their curriculum binders. Families are then given their “home practice,” which is a task that the families do together during the intervening week. The facilitators collect the curriculum binders after each session to bring back to the families the next week.

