The research team will log onto the secure password protected laptop to provide access for the adult participant to take the self-administered pre-web-based survey instrument. For the child participant, a local TRT or UNM research team member will again log onto the secure password protected laptop to administer the pre-web-based survey instrument by reading aloud each question to the child, who will have the laptop with the web-based survey to record each response directly onto the web-based survey behind a desk-top partition, assuring privacy. Once the adult and child pre- web-based surveys are completed the research team member will sign out of the program and shut down the laptop. The consent forms will be collected and placed in a separate sealed envelope and will be transported to UNM in Albuquerque and placed in a different locked filing cabinet in the same locked office of the PI for three years, after which time they (consent forms) will be destroyed according to university procedures in the destruction of hard copies of research documents.

The administration of the post-survey will be conducted at the completion of the twelve week two-hour sessions of the FL/CP prevention/intervention program, and 1yr later and will follow the same steps taken in the administration of the pre-survey as outlined above for both the adult and child participant.—A comparison between pre/post and one year post survey will be conducted by t-testing of comparisons. Findings with statistical significance will be reported and an executive summary will be included. The research team will utilize a participatory approach and engage the tribal research team in the interpretation of the initial findings. Data will be interpreted by the UNM and Tribal Research Teams to ensure cultural appropriateness and reflection of the lived experience of community partners. Dissemination of findings for each community will be based on recommendation by the tribal research team. Past research experience with other tribal communities recommended the preparation of powerpoint slides with findings and brief executive summaries to be shared with tribal leadership and program staff.

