This R01 therefore: 1) supports multilevel understanding and assessment of the FL/CP prevention effectiveness through a quasi-experimental comparison between intervention and comparison children, with triangulation of quantitative and qualitative impact and process measures, and assessment of both core evidence-based and specific cultural components; 2) strengthens research skills of our tribal colleagues as co-researchers building upon research capacities gained from previous CDC and NARCH funded projects; 3) supports a within-tribe longitudinal (pre-post, 6-month post, and 1-year post) that compares program impacts on 4th grade children, their parents and families; and 4) enables an aggregated sample for testing FL/CP effectiveness with sufficient numbers to achieve statistical significance, given effect sizes for preliminary data; and as a scientific inquiry into the role of CBPR in translational research to reduce disparities in Indian country.

As Cook and Campbell (1979) note, there are a wide variety of factors that make the use of randomization procedures in group designs difficult to impossible, especially in field research settings. In the present case, there are a number of factors at work that make the randomization of participants to either an intervention or usual and customary treatment group not feasible. First, the tribal communities that are participating in the proposed

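### The only named test is a t-test, which makes no allowance for program families being treated in 12 shared groups, and the sufficiency statement gives no inputs

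*Combined protocol and SAP*

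**What the plan says.** **Delivery.** Section 10 describes the program this way: "The program is a dinner program with four facilitators and 12 families (child/parent/invited elders) held in tribal facilities". Section 11(d) adds joint facilitation of twelve sessions ("Each year, at least two trained facilitators will participate (overseeing the facilitation"). In the example session in Section 11(e), children and adults work apart and "then they get back together as a whole group of 12 families to share their visions from different generational perspectives".

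**Numbers.** Section 6 gives "12 Program Families (12 families X 3 tribes X 4 waves = 144 families", and the same for comparison families. One group of 12 per tribe and wave makes 3 × 4 = 12 delivery groups; the plan does not state that count, but it follows. Comparison families (Sections 5 and 7) take the surveys and attend no sessions.

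**Analysis.** Section 14 says "A comparison between pre/post and one year post survey will be conducted by t-testing of comparisons". It does not say whether the tests are within or between arms. Section 21 describes a two-arm non-equivalent control group design, defers to a cited methods text for its analysis, and promises a diffusion analysis under Aim 3. It names no model and no grouping factor, and no Aim 3 analysis follows.

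**Adequacy.** Section 21 says the study "enables an aggregated sample for testing FL/CP effectiveness with sufficient numbers to achieve statistical significance, given effect sizes for preliminary data". No effect size, SD, alpha, power or ICC appears anywhere in the document.

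**The concern.** Families who spend twelve sessions together with the same facilitators, and whose interaction is part of the program, may end up with correlated outcomes. A t-test on families gives each one full weight as independent information. With positive correlation inside groups, the program mean is less certain than the t-test assumes, so a true null is rejected too often and intervals are too narrow. The grouping is on one side only, so the analysis has to treat the two arms differently.

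The sufficiency statement matters for a related reason. Without a stated effect size, alpha and power, a reader cannot judge whether 144 against 144 families is enough under any analysis, with or without grouping.

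**Working it through.** **The plan's own count.** 48 participants × 3 tribes × 4 waves = 576, and 12 × 3 × 4 = 144 families per arm. Both reproduce, but they are headcounts. The sufficiency statement cannot be recomputed because its inputs are absent.

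**Inputs.** From Section 6: m = 12 families per group, J = 12 groups (derived), N = 144 families per arm. Assumed: two-sided 5%, 80% power, total variance 1, one outcome per family, full retention. Let g be the ICC of delivery groups (program arm only) and s the share of variance common to both arms in a tribe-by-wave cell.

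**Type I error of a between-arm t-test.** The shared part cancels from the difference in means:

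- true variance = [(1 − s) + 11g]/N + (1 − s)/N = (2 − 2s + 11g)/N
- variance assumed by the t-test ≈ 2/N
- ratio R = 1 − s + 5.5g
- type I error = 2 × [1 − Φ(1.96/√R)]

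| g | R, s = 0 | Type I | R, s = 0.10 | Type I |
|---|---|---|---|---|
| 0.02 | 1.110 | 6.3% | 1.010 | 5.1% |
| 0.05 | 1.275 | 8.3% | 1.175 | 7.1% |
| 0.10 | 1.550 | 11.5% | 1.450 | 10.4% |

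With s = 0.15 and g = 0.02, R = 0.96 and the error is about 4.55%, below nominal. For s = 0, a simulation of 200,000 trials gave 6.33%, 8.25% and 11.48% for the t-test, and 5.01%, 5.04% and 5.05% for a one-sample t-test on the 12 program-minus-comparison cell differences.

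**Detectable effect for the 12-difference test.** Here the scale is the SD of the pretest-adjusted outcome after cell effects are removed.

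- variance of one cell difference = (1 + 11g)/12 + 1/12
- variance of the mean of 12 differences = (2 + 11g)/144
- detectable effect = (t₀.₉₇₅,₁₁ + t₀.₈₀,₁₁) × √[(2 + 11g)/144], with 2.201 + 0.876 = 3.077

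| g | Standard error | Detectable effect | With 10 families per group in each arm |
|---|---|---|---|
| 0 | 0.118 | 0.363 SD | 0.397 SD |
| 0.02 | 0.124 | 0.382 SD | 0.415 SD |
| 0.05 | 0.133 | 0.409 SD | 0.440 SD |
| 0.10 | 0.147 | 0.451 SD | 0.478 SD |

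The last column uses (2 + 9g)/120. Section 6 expects 1 to 3 families to leave each program group out of 13 or 14 recruited, so 10 is its low end (13 − 3); applying 10 to the comparison arm as well is an assumption. For comparison, a t-test on 144 against 144 independent families has a detectable effect of 0.331 SD.

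**The case against.** This is an ethics-board submission, not a full SAP. The t-test sentence sits in a data-handling section, and Section 21 points to a methods text and to an Aim 3 analysis that does not appear. An adjusted analysis may therefore have been intended. That stands: a reader might infer that t-tests are the whole plan, and the documents do not establish this. What they do show is that no method for grouping is described.

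The harm also rests on an assumed ICC. Both arms come from the same fourth grades in close-knit communities, and the plan itself expects diffusion to comparison families, so shared variance is plausible and can remove the inflation. That stands too, and it is why both sets of figures are given. A reader might take Section 14 as a pre/post test inside the program arm, where R = 1 + 11g and the error at g = 0.10 would be 17.6%. Section 14 does not say that this is the test, and the ICC needed there is that of change scores, which may differ.

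A reader might also infer that the number of groups is unsettled, because Section 6 says "from Fiscal Years 1, 2, 3, and 4 only (3 data collection waves total". It is not seriously in doubt. The same sentence gives 576 participants, which needs four waves; three would give 48 × 3 × 3 = 432. The footnote to Table 2 says "Each data collection wave (4 Waves totaling 288 families) includes three data collection points", and Sections 9 and 19 also use four years. The three-wave wording is a slip.

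Finally, a mixed model is only one reasonable choice among several, and self-selection into arms may be a larger threat. Both are true; neither supplies a method for the grouping.

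**Conclusion.** The point holds as an omission with a plausible consequence of uncertain size. Group delivery is explicit, the one named test ignores it, and nothing else in the document describes an allowance for it. Under the assumptions above, type I error at ICC 0.02 to 0.10 runs from about 6.3% to 11.5% with no shared variance, and from about 5.1% to 10.4% with a shared share of 0.10; more sharing can take it below 5%.

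Two stronger conclusions are not supported. The first is that the sample is too small. No effect size is stated, so the sufficiency claim is unsupported but may be right. The second is that the t-tests are certain to mislead. That depends on an ICC and a shared share that the documents do not give. Confidence is high in the omission and lower in the size of its effect. It should be fixed before analysis.

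**What to change.** **Section 14.** Replace the t-tests with a between-arm comparison of post-test and one-year scores, adjusted for the pretest, separately for children and parents. It should allow for tribe-by-wave cells in both arms and for delivery group in the program arm, with small-sample degrees of freedom. A one-sample t-test on the 12 pretest-adjusted program-minus-comparison cell differences (11 df) is a simple and conservative way to do this. State that conclusions apply to these three tribes: the curricula are tribe-specific, and the analysis does not allow for further variation in the program effect between tribes.

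**Section 21.** Give the pilot effect size, alpha and power relied on, and the detectable effect that matches the chosen analysis. For the 11-df test these are about 0.36 / 0.38 / 0.41 / 0.45 SD at assumed ICC 0 / 0.02 / 0.05 / 0.10, stated with their scale (SD of the pretest-adjusted outcome after cell effects) and with full retention. A pilot effect in raw SD units is not directly comparable. If a mixed model is chosen, its detectable effect must be worked out for that model.

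**Cost.** Wording only. The ID code in Section 25 already carries tribe, wave and family with study group. On the same scale, intervals widen and the detectable effect at ICC 0.02 rises from 0.33 to 0.38 SD; about 0.03 of that step (0.331 to 0.363) is the price of the 11-df test even when the ICC is zero.

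**Separate editorial correction, Section 6.** Make the three-wave wording agree with the four waves used elsewhere.

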Through CBPR, to support the three Tribal Research Teams (TRTs) to transform their research capacities into local prevention research infrastructures and a shared partnership. Building from the strengths of UNM-CPR’s partnership with Jemez to help coordinate the 3 tribes in the trial, each TRT will receive trainings in advanced CBPR and prevention science, with annual collaborative face-to-face TRT meetings to share lessons learned and support local tribal structures for future prevention research and programs. A novel CBPR conceptual model will guide evaluation of UNM-CPR and TRT partnership processes to assess effectiveness in fulfilling grant objectives and in reducing substance abuse.

Aim Three:

Assess additional program effects on other health, education and youth programs and leaderships within the three tribes. The FL/CP has potential for deep cultural embeddedness and community integration into other health and education prevention programs. We plan to assess knowledge about FL/CP and effects on tribal programs and leadership by interviewing people with varying degrees of closeness. Through interviews with program managers, staff educators, and tribal leaders, we will assess implementation and diffusion outcomes, such as potential for sustainability, pathways of information exchange, level of integration of curriculum into other programs, and multi- program collaboration.

In sum, the tribes and the University of New Mexico Center for Participatory Research are building on committed CBPR partnerships to test the effectiveness of our innovative culturally-centered evidence-based and empowerment intervention with its integrated theoretical model. This grant provides an opportunity to reduce substance abuse in three tribes, to strengthen research capacity among tribal partners for future prevention research and programs, and to make a difference in substance abuse prevention research

designs nationally, showcasing how CBPR can integrate evidence-based interventions with cultural-specific contexts. Our FL/CP intervention, consisting of a CBPR process, that reintegrates culture into an evidence-based core, will then be available as a key model for other tribes across the nation.

4) Background

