- f) Process data will be collected during program implementation. Our well-tested process instruments include: journals by children and parents as the last activity of each session, facilitator logs as to activities completed and quality of interaction observed, and discussion groups at mid-point and at the end of the Program.
- g) In YR01, for the third research aim of the grant, each TRT will collaboratively identify key individuals within each tribal setting, where program diffusion will be most evident, i.e. those with the strongest program links to FL/CP, such as educators who teach next to teachers who are facilitators in the Program, or other Program leaders who work with youth. From YR01 though YR05, we will annually interview 4 individuals (see Attachment C: Interview Guide) in each tribe to qualitatively assess what interviewees know and have learned about FL/CP; the extent to which they have incorporated ideas from FL/CP into their programs or classes (managers, staff, teachers) or decision-making (leadership); and if collaboration on substance abuse issues has increased with time through the diffusion processes.
- h) In YR01- YR05, TRTs will conduct an annual scan (through interviewing the school and/or youth program key informant, as part of the five interviewees) to identify other substance abuse prevention programs, culture and language programs, or integration of FL/CP cultural components into tribal programs to be able to plot these other resources against the FL/CP impacts. This scan will first take place at baseline. Rather than trying to prevent cross-contamination, we expect there will be diffusion of FL/CP program components as well as increased knowledge by other Health and Education staff and educators to create an environment where FL/CP can be sustainable to improve health and reduce substance abuse over the long term (beyond when the grant ends).
- i) Co-analysis of pre/post-test and process evaluations will be conducted
- j) Dissemination plan will be co-developed.

12) List of Appendices

- Attachment A: Family Program Recruitment Letter
- Attachment B: Study Timeline
- Attachment C: Tribal Leader and Managers' Interview Guide

13) Data and Specimen Banking

No data or specimens will be banked.

14) Data Management

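### Aim Three needs interviewees at varying closeness to FL/CP, but item g of section 11 points to those most strongly linked; if followed, it removes any comparison by closeness

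*Combined protocol and SAP*

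**What the plan says.** Three places in the protocol describe who is interviewed for Aim Three.

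- **Section 3, Aim Three**, sets the principle: "We plan to assess knowledge about FL/CP and effects on tribal programs and leadership by interviewing people with varying degrees of closeness". From interviews with managers, staff educators and leaders, "we will assess implementation and diffusion outcomes, such as potential for sustainability, pathways of information exchange", along with integration into other programs and collaboration between programs.
- **Section 7, paragraph on leaders, managers, educators and staff**, describes a review of community organizations and of prevention and youth programs: "From this review of programs, the pool of managers and educators will be identified". It adds that community or traditional leaders may lie outside any program and will be reached through the TRT members' own connections.
- **Section 11, item g**, written expressly for the third aim, gives the working instruction: "each TRT will collaboratively identify key individuals within each tribal setting, where program diffusion will be most evident". It then defines those individuals as "those with the strongest program links to FL/CP, such as educators who teach next to teachers who are facilitators in the Program", with other program leaders working with youth as a second example. On number, "we will annually interview 4 individuals" in each tribe, from YR01 through YR05.

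Section 11, item h, adds an annual scan through a key informant who is counted among five interviewees. Section 14 says the interviews will be coded inductively and analysed by theme.

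**The concern.** Item g chooses people by something very close to what the interviews are meant to find out. They ask what people know about FL/CP, how far they have taken its ideas into their programs or decisions, and whether collaboration has grown through diffusion. Choosing people where diffusion is expected to show most selects for favourable answers to the first two questions in particular.

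Two things are at stake. The first is the contrast that Aim Three promises: without people distant from the program, nobody can say whether knowledge and uptake fade with distance. The second is generalisation. Accounts from the facilitators' nearest colleagues could be read as describing spread through a tribe's programs and leadership as a whole. Item h plans to set other prevention resources, and FL/CP components adopted elsewhere, against FL/CP impacts, so a picture of diffusion drawn from close colleagues could also colour how the main results are discussed. That last step is inference; the protocol does not say it will happen.

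**Working it through.** No power, sample-size or error-rate figure applies to this aim, so the check is mainly a comparison of texts.

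**1. Selection rules side by side**

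| Place | Who is interviewed | Closeness criterion |
|---|---|---|
| Section 3, Aim Three | Managers, staff educators, leaders | A range of closeness |
| Section 7 | Managers and educators from a program review; leaders, possibly unaffiliated | None stated |
| Section 11, item g | Key individuals named by each TRT | Strongest links |

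**2. Can all three be followed together?** Item g reads "where program diffusion will be most evident, i.e. those with the strongest program links to FL/CP". The *i.e.* makes strongest links the definition of the people sought; the examples after it illustrate that definition. A team applying it literally would not produce the range that Aim Three describes. Section 7 could supply that range, but it sets no closeness groups, no minimum for distant people and no rule for moving from its pool to the annual interviewees. Item g is the only place that turns closeness into a selection instruction, and it runs in one direction.

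**3. Do other sources supply the contrast?** The item h scan starts at baseline and covers other programs, which helps. Its key informant, however, belongs to the same interviewee set. The diffusion analysis in section 21 concerns comparison families, not tribal programs and leadership.

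**4. Direction of any lean.** Let *s* be the share of eligible people with strong links, and *d* the difference in uptake between strongly linked people and the rest. If only strongly linked people were interviewed and the result were read as applying to everyone, the excess would be (1 − *s*) × *d*. This is positive whenever *s* is below 1 and uptake is higher among the strongly linked, which is the premise of item g. The documents give neither quantity and plan no uptake rate, so only the direction can be stated.

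**5. Number of interviews.** The documents state no total. With 3 tribes and 5 years (YR01 to YR05):

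- item g: 4 × 3 = 12 per year; 12 × 5 = 60
- item h: 5 × 3 = 15 per year; 15 × 5 = 75

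These count interviews. Item g does not say whether the same individuals return each year.

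**The case against.** The strongest defence is that purposive selection of well-informed people is accepted in qualitative work, and section 29 describes recruitment as purposeful. Well-placed informants can speak to sustainability, information pathways, integration and collaboration. Item g also asks whether collaboration has grown over time, and a strong link to the program does not guarantee a yes. The educators in its example are one step removed from delivering the sessions. Section 7 allows for unaffiliated leaders, and item g itself lists leadership among those whose use of FL/CP ideas is assessed.

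Most of this stands, and it rules out three stronger readings that a reader might infer:

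- **That the protocol interviews strongly linked people and nobody else.** Section 7 does not exclude distant people; it merely fails to guarantee them. The plan is inconsistent rather than uniformly restricted.
- **That measured diffusion will be overstated.** No diffusion rate is defined. A lean arises only if findings are carried beyond the people interviewed.
- **That Aim Three cannot be answered.** Change, integration and sustainability among those interviewed can still be described, and the annual scan adds information.

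What the defence does not remove is the conflict itself. Purposive sampling should serve the stated purpose, and here the purpose is a range of closeness while the instruction seeks one end of it.

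**Conclusion.** The conflict between Aim Three and item g is real and plain from the text, and section 7 does not resolve it. If item g is followed, the planned 60 interviews (75 if item h's count governs) would come from people strongly linked to FL/CP. Findings then could not be compared by closeness, and any statement about the extent of diffusion across tribal programs and leadership would probably lean upward. The upward direction assumes that knowledge and uptake are greater among strongly linked people, as item g itself supposes, and that results are generalised beyond them. Its size cannot be determined from the documents.

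The point is confined to a qualitative aim; it does not alter the Aim One comparison of intervention and comparison families. It is still worth correcting, because a written instruction works against the aim it serves.

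**What to change.** Amend item g as follows:

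1. Draw interviewees from the section 7 pool, with leaders included.
2. Classify each candidate's link to FL/CP (for example strong, some or none) before selection.
3. Reserve a minimum number of weakly linked or unlinked people per tribe, and keep it constant every year so that rounds are comparable.
4. Report themes by closeness.

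The documents give no basis for a particular minimum; the teams should set it. With four interviews per tribe per year, reserving one gives 1 × 3 × 5 = 15 of the 60, and reserving two gives 2 × 3 × 5 = 30. Either is thin within a single tribe and year, so the comparison by closeness would rest mainly on interviews taken together across years.

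If the teams prefer to keep item g's rule, Aim Three should be reworded so that its conclusions are limited to people closely linked to the program. In either case, items g and h should state the same annual number per tribe.

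The cost is a paragraph of wording and a classification of the candidate list, with no extra interviews needed. The drawback of the first option is fewer interviews with well-informed insiders.
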